65 obstruction prior to surgery. This represents the first biliary metal stent with labeling to support  
66 pre-operative drainage in the US.

67 **1.4 Preclinical Data**

68 Please see clinical data below

69 **1.5 Clinical Data to Date**

70 A recent meta-analysis of 1989 patients showed that SEMS have higher stent insertion success,  
71 lower risk of stent occlusion, lower re-intervention rate, fewer therapeutic failures, and fewer  
72 episodes of cholangitis compared to plastic stents making them the optimal choice for biliary  
73 decompression.[8] Also a recent randomized controlled trial confirmed that SEMS are superior to  
74 plastic stents with regard to functional stent time and showed that the total health care cost is  
75 similar for placing SEMS or plastic stents even in patients with survival less than 3 months

76 **1.6 Dose Rationale and Risk/Benefits**

77 The study doesn't involve drug administration.

78 **2.0 STUDY OBJECTIVES**

79 **2.1 Primary Objective:**

80 The primary aim of this study is to compare the 30 and 90-day overall complication rates between  
81 patients with severe obstructive jaundice undergoing preoperative endoscopic biliary drainage  
82 with SEMS and patients undergoing direct surgical resection.

83 **2.2 Secondary Objective:**

84 Secondary aims will be to compare surgical outcomes including hospital length of stay, ICU  
85 length of stay, readmission rate, disposition from hospital, emergency room visits, urgent care  
86 center visits and time to commencement of adjuvant treatment.

87 **3.0 STUDY DESIGN**

88 **3.1 General Design**

89 This is a Randomized controlled trial.

92 ERCP will be performed on those who are randomized to the intervention group with 24 hours of  
93 randomization. The patient will be followed at 30 days and 90 days post-operatively.

94 **3.2 Primary Study Endpoints**

95 30 and 90 day- complication rates between patients with severe obstructive jaundice undergoing  
96 preoperative endoscopic biliary drainage with SEMS and patients undergoing direct surgical  
97 resection

98 **3.3 Secondary Study Endpoints**

99 Secondary aims include the total number of complications, intraoperative estimated blood loss,  
100 number of required fluid boluses, postoperative hospital LOS, readmission rate, disposition from  
101 hospital, time to commencement of adjuvant treatment, emergency room visits, urgent care center  

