170 The stent will placed by ERCP and won't be removed before surgery unless indicated. Follow up  
171 phone calls to ascertain secondary endpoints will be made at 30 and 90 days.

172 5.7 Prior and Concomitant Therapy  
173 Subject in the study are to continue any medications that they are on. Those who are randomized  
174 to the intervention group may be asked to hold antiplatelet/anticoagulation agents prior to the  
175 ERCP in coordination with their prescribing doctor.

176 5.8 Blinding of Study Drug  
177 Unblinded study

178 **6.0 STUDY PROCEDURES**

179

180 **6.1 Study Visit Schedule**

181 **Screening:**  
182 Patients will be screened in clinic or if admitted as inpatients. Patient must satisfy the inclusion  
183 criteria listed above. Patient must carry a diagnosis of per-ampullary cancer. Basic labs will be  
184 withdrawn including CBC, CMP and INR.

185

186 **Randomization**  
187 **Peri-operative:** The patient will be admitted and labs will obtained including CBC, CMP and  
188 INR prior to surgery.

189

190 **Post-operative:**  
191 Visit 1: This will be scheduled 3-4 weeks after hospital discharge. Labs and imaging may be  
192 ordered by the surgeon if needed.

193 Follow-up  
194 Patients will be followed up to 90 days after the surgery. A phone call will be placed to the  
195 patient by research staff to ascertain secondary endpoints. Jefferson EMR will be accessed  
196 to ascertain primary endpoint data.

197

198 **7.0 STATISTICAL PLAN**

199 7.1 Sample Size Determination  
200 Based on previous data, we assumed an overall grade III or higher complication rate of  
201 50% in the control group. Although we are unsure of the expected rate in the pre-operative  
202 biliary stenting group, a 30% or greater reduction in the grade III or higher complication

would be meaningful. The sample size will be 100 subjects (50 per arm). We calculated power under various alternatives for the biliary stenting group complication rate using a two-group large-sample normal approximation test of proportions, with a one-sided significance level of 0.05, to test the null hypothesis that the grade III or higher complication rate in surgery with biliary stenting is greater than or equal to the control rate (50%). We have 84% power to detect a reduction if the true rate with biliary stenting is 25%, 66% power if the true rate is 30%, and 44% power if the true rate is 35%.

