## 7.2 Statistical Methods

Baseline characteristics will be summarized by randomization arm using means, standard deviations, and ranges for continuous variables and counts and frequencies for categorical variables.

Rates of grade III or higher complication rates will be estimated separately at 30 and 90 days. The risk difference will be calculated (stent minus control) with a one-sided 95% confidence interval. If the upper bound of the confidence interval is less than 0 at both times, surgery with biliary stenting will be considered effective at reducing the rate of grade III or higher complications.

Group comparisons with respect to continuous outcomes will be performed using two-sample t-tests or Wilcoxon rank sum tests. Comparisons for categorical outcomes will be performed using chi-square tests or Fisher's exact test. Comparisons for count outcomes will use Poisson regression. Kaplan-Meier analysis will be used to estimate the distribution of time-to-event outcomes. Groups will be compared using the log rank test.

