279           the last scheduled visit, the investigator should instruct each subject to report any  
280           subsequent event(s) that the subject, or the subject's personal physician, believes might  
281           reasonably be related to participation in this study. The investigator should notify the study  
282           sponsor of any death or adverse event occurring at any time after a subject has discontinued  
283           or terminated study participation that may reasonably be related to this study. The sponsor  
284           should also be notified if the investigator should become aware of the development of  
285           cancer or of a congenital anomaly in a subsequently conceived offspring of a subject that  
286           has participated in this study.

287           Abnormal Laboratory Values

288           A clinical laboratory abnormality should be documented as an adverse event if any one of  
289           the following conditions is met:

290           • The laboratory abnormality is not otherwise refuted by a repeat test to confirm the  
291           abnormality  
292           • The abnormality suggests a disease and/or organ toxicity

293           • The abnormality is of a degree that requires active management; e.g. change of  
 294           dose, discontinuation of the drug, more frequent follow-up assessments, further  
 295           diagnostic investigation, etc.

296           Hospitalization, Prolonged Hospitalization or Surgery

297           Any adverse event that results in hospitalization or prolonged hospitalization should be  
 298           documented and reported as a serious adverse event unless specifically instructed otherwise  
 299           in this protocol. Any condition responsible for surgery should be documented as an  
 300           adverse event if the condition meets the criteria for an adverse event.

301           Neither the condition, hospitalization, prolonged hospitalization, nor surgery are reported  
 302           as an adverse event in the following circumstances:

- 304           • Hospitalization or prolonged hospitalization for diagnostic or elective surgical  
 305           procedures for a preexisting condition. Surgery should **not** be reported as an  
 306           outcome of an adverse event if the purpose of the surgery was elective or  
 307           diagnostic and the outcome was uneventful.

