- 308           • Hospitalization or prolonged hospitalization required to allow efficacy  
 309           measurement for the study.
- 310           • Hospitalization or prolonged hospitalization for therapy of the target disease of the  
 311           study, unless it is a worsening or increase in frequency of hospital admissions as  
 312           judged by the clinical investigator.

313           8.2 Recording of Adverse Events

314           At each contact with the subject, the investigator must seek information on adverse events by  
 315           specific questioning and, as appropriate, by examination. Information on all adverse events  
 316           should be recorded immediately in the source document, and also in the appropriate adverse event  
 317           module of the case report form (CRF). All clearly related signs, symptoms, and abnormal  
 318           diagnostic procedures results should be recorded in the source document, though should be  
 319           grouped under one diagnosis.

320           All adverse events occurring during the study period must be recorded according to the following:

Adverse event	Start date	SAE* 1. Yes (also complete SAE form) 2. No	Causality 1. Unrelated 2. Possibly Related	Severity 1. Mild 2. Moderate 3. Severe	Expectedness 1. Expected 2. Unexpected	DATE of assessment and INITIALS of delegated clinician	Outcome 1. Resolved 2. Ongoing	Date Resolved	AE Recorded by (initials)

324  
325  
326 The clinical course of each event should be followed until resolution, stabilization, or until it has  
327 been determined that the study treatment or participation is not the cause. Serious adverse events  
328 that are still ongoing at the end of the study period must be followed up to determine the final  
329 outcome. Any serious adverse event that occurs after the study period and is considered to be  
330 possibly related to the study treatment or study participation should be recorded and reported  
331 immediately.

332 **8.4 Stopping Rules**

333 We will do an interim analysis after reaching 50 patients, and if there is a significant  
334 difference (> 20%) in post operative mortality or morbidity in one group versus the other,  
335 then the study will be discontinued.

336 **8.5 Data and Safety Monitoring Plan**

337 It is the responsibility of the Principal Investigator to oversee the safety of the study at his/her  

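### The plan takes the primary endpoint from the Jefferson EMR and does not say that grade III or higher complications treated elsewhere, and learned of by call or AE report, are counted

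*Combined protocol and SAP*

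**What the plan says.** **Source of the primary endpoint.** Under Follow-up, section 6.1 has a call made to the "patient by research staff to ascertain secondary endpoints. Jefferson EMR will be accessed" "to ascertain primary endpoint data". No other source is named for the primary endpoint. Section 5.6 agrees on the calls: "phone calls to ascertain secondary endpoints will be made at 30 and 90 days".

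**How the trial is decided.** Section 7.2 estimates grade III or higher complication rates at 30 and at 90 days. It declares stenting effective "If the upper bound of the confidence interval is less than 0 at both times", where the interval is one-sided 95% for stent minus control. Section 7.3 analyzes all randomized patients, and section 7.1 makes no allowance for missed events.

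**What else is collected.**
- Section 3.3: "Secondary aims include the total number of complications, intraoperative estimated blood loss" and, further on, readmissions and "hospital, time to commencement of adjuvant treatment, emergency room visits, urgent care center" visits.
- Section 6.1: one scheduled post-operative visit (Visit 1), 3-4 weeks after discharge.
- Section 8.2: "At each contact with the subject, the investigator must seek information on adverse events by" specific questioning, with answers entered in the source document and CRF. The AE form has three severity levels: mild, moderate and severe.
- Section 8.1: "Any adverse event that results in hospitalization or prolonged hospitalization should be" handled as an SAE, listed exceptions apart. The reporting period runs from randomization to 90 days after surgery.
- Section 8.5.1: AE reporting is based on CTC 4.0.
- Sections 9.2 and 9.3: hospital records are among the source documents, and the CRF is the primary collection instrument.

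**The concern.** A patient may be readmitted or have a procedure at another hospital within 90 days of surgery. Unless this reaches the Jefferson chart, the rule in section 6.1 scores that patient as event-free. The event would not appear as missing data. It would look like a good outcome, and section 7.3 would carry it into the analysis. The same event could meanwhile be recorded as a readmission among the secondary endpoints and as an SAE, so the trial could know of it and still leave it out of the deciding count.

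Equal loss in both arms shrinks the risk difference and lowers power. Unequal loss biases the comparison, in a direction that depends on which arm loses more.

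**Working it through.** **1. Is there a link from the other sources to the primary count?** The calls cover readmissions, emergency and urgent care visits and total complications, but sections 5.6 and 6.1 assign them to secondary endpoints. AE questioning and SAE reporting can reveal an outside event, but no sentence ties them to the grade III or higher count, and the AE form's three levels would have to be regraded. Visit 1 may put an early outside event into the Jefferson chart. It falls on post-operative day 21-28 plus length of stay. Stay is not given; with an assumed 2-9 days or more, the visit comes around or after day 30 (28 + 2 = 30; 21 + 9 = 30). It is the only scheduled visit, so it does not cover the rest of the 90 days. Detection is therefore plausible, but counting is not specified.

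**2. The plan's own power.** Inputs from section 7.1: 50 per arm, control rate pc = 0.50, one-sided alpha 0.05. With p̄ the mean of the two rates:

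Power = Φ[(pc − ps − 1.645·SE0)/SE1], SE0 = √(2p̄(1−p̄)/50), SE1 = √((pc(1−pc) + ps(1−ps))/50).

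For ps = 0.25: SE0 = √(2×0.375×0.625/50) = 0.0968; SE1 = √((0.25 + 0.1875)/50) = 0.0935; (0.25 − 0.1593)/0.0935 = 0.970; power 83.4%. For ps = 0.30 and 0.35 the results are 65.7% and 44.9%. The plan states 84%, 66% and 44%, so its figures reproduce.

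If a share m of events is missed in both arms, each rate is multiplied by (1 − m). At m = 10% the rates become 0.45 and 0.225, the difference falls from 25 to 22.5 points, and single-time power falls from 83.4% to 77.5%.

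**3. Under the rule that decides the trial.** Section 7.2 requires success at both times, so the calculation was repeated exactly for that rule. In each arm X30 ~ Bin(50, p30) and X90 = X30 + Bin(50 − X30, (p90 − p30)/(1 − p30)). Success means that the unpooled Wald one-sided 95% upper bound is below 0 at both times.

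Assumptions: control p90 = 0.50 (section 7.1 gives 50% without saying 30 or 90 days); control p30 = 0.30, 0.35 or 0.40; for power, stent rates are half the control rates; for false success, both arms have the same true rates. All missed shares are assumed.

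| Scenario | p30 = 0.30 | 0.35 | 0.40 |
|---|---|---|---|
| Power, no loss | 55.7% | 62.7% | 70.1% |
| Power, 5% missed in both arms | 53.3% | 59.9% | 66.9% |
| Power, 10% missed in both arms | 50.7% | 57.1% | 63.6% |
| Power, 20% missed in both arms | 45.3% | 51.3% | 57.1% |
| Power, 10% missed, control arm only | 41.2% | 46.9% | 53.2% |
| False success, no loss | 1.7% | 2.1% | 2.5% |
| False success, 5% missed, stent arm only | 2.9% | 3.7% | 4.4% |
| False success, 10% missed, stent arm only | 4.8% | 5.9% | 7.2% |

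**4. Loss confined to after day 30.** Here the observed 90-day rate becomes p30 + (1 − m)(p90 − p30), and the 30-day count is intact. With m = 20% of late events:
- missed in both arms, power is 55.1%, 62.4% and 70.0%, a cost of about 0.5 points at most;
- missed in the stent arm only, false success is 2.9%, 3.2% and 3.3%;
- missed in the control arm only, power is 52.7%, 60.4% and 68.6%, a cost of at most 3.0 points.

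At shares of this order, the loss that matters is loss that reaches the 30-day count.

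**The case against.** The strongest reply is that the plan already gathers most of what is needed. Section 6.1 says that the EMR will be used, not that only the EMR may be used. The CRF, not the EMR, is the main instrument; hospital records count as source documents with no restriction to Jefferson; AEs are asked about at every contact. Visit 1 falls at about the time when an early outside event would most need to be picked up. Section 9.3 refers to a CRF in the appendix, but the available text shows only an AE log there, so a field for outside complications cannot be ruled out. Regrading is a small matter too, since EMR entries must also be graded. At 5% equal loss, power drops by only 2.4 to 3.2 points.

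Much of this stands. A reader might infer that the plan has no means of learning about outside events; Visit 1, the calls and the AE/SAE reporting show otherwise. A reader might also infer that missed events would favor stenting. The documents give no missed fraction and no reason for it to differ by arm, since both arms have the same visit and calls, and control-only loss would work against stenting. Nor do the mentions of participating sites in sections 8.5.2 and 10.2.1 establish that patients will be enrolled elsewhere: the summary lists one center.

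What the reply does not supply is the link. No visible text says that an outside event, once known, is counted.

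**Conclusion.** The point holds as a gap between detecting an event and counting it. As written, the primary endpoint is read from the Jefferson EMR, and a grade III or higher complication known only from a call or an AE/SAE report has no stated place in it.

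The likely size is modest. Inpatient events after the resection are probably charted at Jefferson (an inference; the plan does not say so), which makes the smaller missed shares more plausible. Equal loss of 5% or 10% at both times costs 2.4-3.2 or 5.0-6.5 points of power, in a trial whose both-times power is only 56-70% under the stated assumptions. The one-arm results are bounds, not forecasts. Loss of 10-20% of events after day 30 has little effect.

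These figures rest on assumed missed shares, an assumed 30-day control rate, and reading the plan's 50% as the 90-day rate. This is a worthwhile low-cost improvement, not a defect that invalidates the design.

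**What to change.** Amend sections 6.1 and 5.6 so that the planned 30- and 90-day calls put the same questions to every patient in both arms about complications, procedures and admissions at any hospital. For positive answers, request the outside records where the patient's authorization allows. Its scope cannot be checked in the available text and should be confirmed first.

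Then define the primary endpoint as events in the Jefferson EMR plus record-verified events from the calls, Visit 1 and AE/SAE reports, all graded on the same grade III or higher scale.

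The cost is a few extra questions on calls already planned, occasional record requests, some grading time for existing staff in an unfunded study, and possibly a change to the authorization wording. No extra visits are needed.

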## 7.2 Statistical Methods

Baseline characteristics will be summarized by randomization arm using means, standard deviations, and ranges for continuous variables and counts and frequencies for categorical variables.

Rates of grade III or higher complication rates will be estimated separately at 30 and 90 days. The risk difference will be calculated (stent minus control) with a one-sided 95% confidence interval. If the upper bound of the confidence interval is less than 0 at both times, surgery with biliary stenting will be considered effective at reducing the rate of grade III or higher complications.

Group comparisons with respect to continuous outcomes will be performed using two-sample t-tests or Wilcoxon rank sum tests. Comparisons for categorical outcomes will be performed using chi-square tests or Fisher's exact test. Comparisons for count outcomes will use Poisson regression. Kaplan-Meier analysis will be used to estimate the distribution of time-to-event outcomes. Groups will be compared using the log rank test.

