39        potentially biased. Many of the prior studies used plastic stents for preoperative decompression,  
40        which when compared to self-expanding metal stents (SEMS) result in greater rates of re-  
41        intervention and cholangitis. A recent meta-analysis of 1989 patients showed that SEMS have  
42        higher stent insertion success, lower risk of stent occlusion, lower re-intervention rate, fewer  
43        therapeutic failures, and fewer episodes of cholangitis compared to plastic stents making them the  
44        optimal choice for biliary decompression.[8] Also a recent randomized controlled trial confirmed  
45        that SEMS are superior to plastic stents with regard to functional stent time and showed that the  
46        total health care cost is similar for placing SEMS or plastic stents even in patients with survival  
47        less than 3 months.[9] Thus, this study will provide unique perspective on the potential  
48        advantages of biliary decompression using SEMS. Additionally, prior studies have excluded  
49        severely jaundiced patients (serum bilirubin > 14.6), a population that may have derived the

50 greatest benefit from preoperative drainage, since these patients are more likely to have impaired  
51 liver function. In fact, patients with malignant obstruction who present with severe jaundice  
52 ( $>10\text{mg/dL}$ ) are likely at higher risk for poor outcome following surgery.[10] These patients may  
53 also benefit from preoperative drainage to alleviate pruritus and correct coagulation  
54 disturbances.[11] Thus, although preoperative biliary drainage may not be routinely  
55 recommended for all patients with malignant biliary obstruction, drainage may be potentially  
56 advantageous for those patients with severe jaundice using a SEMS.

57 **1.3 Study Therapy**

58 Both preoperative SEMS placement and direct surgical resection are considered acceptable  
59 standard of care in this patient population.

60  
61 SEMS (Wallflex, Boston Scientific) will be used. The WallFlex Biliary Stent System is FDA-  
62 cleared in the US, and is indicated for use in the palliative treatment of biliary strictures produced  
63 by malignant neoplasms. Also, the WallFlex Biliary RX Stent is 510(k) cleared for the treatment  
64 of biliary strictures produced by malignant neoplasms and relief of malignant biliary  

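### The primary risk difference is unadjusted and randomisation unstratified, although screening bilirubin is known for every patient; pre-specified adjustment would be a modest, low-cost gain in efficiency

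*Combined protocol and SAP*

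**What the plan says.** - **Primary analysis (section 7.2).** "The risk difference will be calculated (stent minus control) with a one-sided 95% confidence interval". Stenting is declared effective "If the upper bound of the confidence interval is less than 0 at both times", that is, at 30 and at 90 days. No covariates are named; baseline data are only described by arm.
- **Randomisation (section 5.4).** Random permuted blocks, with no stratification factor named.
- **Baseline data (sections 4.1, 4.4 and 6.1).** Entry requires bilirubin above 10 mg/dL, with no upper limit, so a value exists for every patient. Screening blood tests are listed as "withdrawn including CBC, CMP and INR". The same tests are repeated before surgery, after randomisation.
- **Prognosis (section 1.2).** Patients with severe jaundice, defined there as above 10 mg/dL, "are likely at higher risk for poor outcome following surgery.[10] These patients may" gain from drainage through relief of itching and better coagulation. The section also notes that earlier studies left out patients above 14.6, who are said to be more prone to impaired liver function.
- **Power (section 7.1).** 50 patients per arm, control rate 50%, and a "two-group large-sample normal approximation test of proportions, with a one-sided significance level of 0.05". Stated power is 84%, 66% and 44% for stent-arm rates of 25%, 30% and 35%.

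**The concern.** The trial exists because high bilirubin is thought to raise surgical risk, yet neither the randomisation nor the primary analysis uses the bilirubin value. If bilirubin predicts grade III or higher complications among enrolled patients, adjusting for it narrows the confidence bound without adding patients or measurements. It also takes out the part of the treatment estimate that is due to chance imbalance in bilirubin.

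Power is limited at the smaller effects considered. Section 7.1 calls a reduction of 30% or more meaningful without saying whether that is relative or absolute. Read as relative (50% to 35%), the stated power is 44%. Success is also required at both time points, so power for the actual decision cannot exceed the lower of the two single-time powers.

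**Working it through.** **Inputs.** From section 7.1: n = 50 per arm, control rate 0.50, stent rates 0.25, 0.30 and 0.35, one-sided alpha 0.05 (z = 1.645). Section 7.1 states no dropout allowance, so none is used. R2, the share of outcome variance explained by the baseline covariates, is not in the documents; it is an assumption, varied from 0 to 0.30. All figures are for one time point.

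**Step 1: reproduce the plan's power.** With p̄ the mean of the two rates,

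power = Φ{[(p0 − p1) − 1.645·√(2p̄(1−p̄)/50)] / √(p0(1−p0)/50 + p1(1−p1)/50)}.

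For 50% versus 30%: √(2 × 0.40 × 0.60/50) = 0.0980, times 1.645 = 0.161. The denominator is √((0.25 + 0.21)/50) = 0.0959. So Φ((0.20 − 0.161)/0.0959) = Φ(0.405) = 65.7%. The same formula gives 83.4% for 25% and 44.9% for 35%. Exact enumeration of the pooled z-test gives 84.0%, 65.8% and 44.0%, which matches the stated 84%, 66% and 44%. The plan's power is therefore for an unadjusted, one-sided test without continuity correction.

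**Step 2: analytic effect of adjustment.** Multiply the variance by (1 − R2), equivalent to 50/(1 − R2) patients per arm. The margin is the distance from the estimate to the one-sided bound, 1.645 × 0.0959 × √(1 − R2) at 50% versus 30%.

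| Assumed R2 | Equivalent n per arm | Power, 25% | Power, 30% | Power, 35% | Margin at 30% (points) |
|---|---|---|---|---|---|
| 0 | 50.0 | 83.4% | 65.7% | 44.9% | 15.8 |
| 0.02 | 51.0 | 84.1% | 66.5% | 45.5% | 15.6 |
| 0.05 | 52.6 | 85.1% | 67.7% | 46.4% | 15.4 |
| 0.10 | 55.6 | 86.7% | 69.8% | 48.2% | 15.0 |
| 0.20 | 62.5 | 90.1% | 74.2% | 52.1% | 14.1 |
| 0.30 | 71.4 | 93.2% | 79.2% | 56.8% | 13.2 |

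At 50% versus 30% the gain is 66.5 − 65.7 = 0.8 points at R2 = 0.02 and 69.8 − 65.7 = 4.1 points at R2 = 0.10.

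**Step 3: simulation.** Step 2 ignores the cost of estimating the covariate effects. A simulation of 6,000 trials per setting, with 100 patients, two baseline covariates, logistic standardisation and an influence-function standard error, includes it. Results at 50% versus 30%:

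| R2 in control arm | Unadjusted power | Adjusted power | Change (points) |
|---|---|---|---|
| 0 | 66.5% | 65.6% | −0.9 |
| about 0.04 | 67.6% | 68.3% | +0.7 |
| about 0.10 | 67.5% | 70.1% | +2.6 |
| about 0.17 | 67.0% | 73.2% | +6.2 |
| about 0.29 | 66.4% | 78.0% | +11.6 |

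Each power has a simulation error of about √(0.67 × 0.33/6000) = 0.6 points. With equal true rates of 50%, the adjusted test rejected in 4.9% to 5.5% of trials and the unadjusted test in 4.1% to 4.8%. Part of the small gains may reflect that difference.

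**Step 4: chance imbalance.** With 50 per arm, the difference between arms in a baseline mean has standard error √(1/50 + 1/50) = 0.20 SD. It exceeds 0.2 SD in about 32% of trials and 0.4 SD in about 5%.

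**The case against.** The strongest reply is that nothing here is wrong with the plan. Randomisation makes the unadjusted risk difference valid, its confidence interval already allows for chance imbalance, and it is the analysis that was powered. All of that stands. Step 4 shows that moderate imbalance is common and large imbalance is not; neither biases the unadjusted analysis.

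The evidence for bilirubin as a covariate is also thin. Section 1.2 describes risk mainly at a threshold that every enrolled patient exceeds. The remark about patients above 14.6 suggests a gradient inside the enrolled range, but it concerns liver function and possible benefit from drainage, and gives no measured association with complications. R2 could be near zero.

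Two stronger readings are tempting, and the documents support neither:

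- *That INR is also described as prognostic.* It is not. Coagulation appears in section 1.2 only as something drainage may correct. Section 5.7 also anticipates antiplatelet or anticoagulant use, so screening INR may partly reflect medication.
- *That the precision is free.* It is not. If the covariates carry no information, adjustment loses about 1 point of power (66.5% to 65.6%).

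What remains is that the likely loss is small, the possible gain is somewhat larger, and the quantity estimated does not change.

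**Conclusion.** The point holds as an optional, low-cost improvement to a valid analysis. For 50% versus 30% at a single time point, the power change is about -1 point with uninformative covariates and about +1 to +4 points for R2 of 0.02 to 0.10 (the simulation lies at the lower end: +0.7 at 0.04, +2.6 at 0.10). It is roughly +6 to +14 points for R2 of about 0.17 to 0.30, and nothing in the documents shows that values this high apply.

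A reader might infer that adjustment would repair the low power at a 35% stent-arm rate. It would not: at R2 = 0.10 power is still 48.2%. Nor does it alter the requirement to succeed at both times.

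**What to change.** Pre-specify in section 7.2, for each of 30 and 90 days:

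- a logistic model with arm and log screening total bilirubin, from which the risk difference (stent minus control) is standardised over all randomised patients, with a robust or delta-method one-sided 95% bound;
- the existing rule, applied to these bounds at both times;
- the unadjusted risk difference as a sensitivity analysis.

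Screening INR may be added but is optional, because the documents do not call it prognostic. Use screening values only: the pre-surgery tests follow randomisation and, in one arm, stenting. Fix the covariates before any outcome comparison, including the interim look at 50 patients in section 8.4, because the study is unblinded.

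**Cost.** A few lines of analysis text and code, with no new data or patients. Reporting becomes slightly more complex, and about 1 point of power is lost if bilirubin has no prognostic value above 10 mg/dL. That figure comes from a model with two covariates; one covariate should cost no more.
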